7.9.5 Additional Endpoints

The percentage of subjects meeting criteria for sexual dysfunction (ie, CSFQ-14 total score ≤ 47 for men and ≤ 41 for women) at any 2 consecutive visits (using LOCF) during the treatment period will be analyzed by logistic regression, adjusting for baseline CSFQ-14 total score, sex, and treatment.

Time to sexual dysfunction as assessed by the CSFQ-14 and time to CSFQ-14 negative response (defined as the decrease from Baseline in CSFQ-14 total score ≥ 3) will be analyzed using a Cox model with an exact method to handle ties, with treatment and sex as factors. The SAS code for the time-to-event analysis will be as follows:

```
proc phreg;
  class treat;
  model T_Sexdys*status_1(0) = treat sex/ ties=exact;
```

The analysis will also be supplemented with plots of Kaplan-Meier estimates of sexual dysfunction.

CSFQ-14 shift from normal (ie, CSFQ-14 total score > 47 for men and > 41 for women) at Baseline to abnormal (ie, CSFQ-14 total score ≤ 47 for men and ≤ 41 for women), and CSFQ-14 negative responders (decrease from Baseline in CSFQ-14 total score ≥ 3) will be analyzed at all visits by logistic regression, adjusting for baseline CSFQ-14 total score, sex, and treatment.

PGI-I will be analyzed by study visit using ANCOVA and LOCF, with treatment, center, and sex as fixed factors. MMRM analysis will also be performed.

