7.5 Procedures for Discontinuation or Withdrawal of a Subject

The investigator may discontinue a subject's study participation at any time during the study when the subject meets the study termination criteria described in Section [7.4](#). In addition, a subject may discontinue his or her participation without giving a reason at any time during the study. Should a subject's participation be discontinued, the primary criterion for termination must be recorded by the investigator. In addition, efforts should be made to perform all procedures scheduled for the ET Visit. Discontinued or withdrawn subjects will not be replaced. Discontinued or withdrawn subjects will receive a Follow-up Contact.

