13.1.3.3 Additional Analyses

The percentage of subjects meeting criteria for sexual dysfunction (ie, CSFQ-14 total score ≤ 47 for men and ≤ 41 for women) at any 2 consecutive visits (using LOCF) during the double-blind Treatment Period will be analyzed by logistic regression, adjusting for baseline CSFQ-14 total score, sex, and treatment.

Time to sexual dysfunction as assessed by the CSFQ-14 will be analyzed using a Cox model with an exact method to handle ties, with treatment and sex as factors.

CSFQ-14 shift from normal (ie, CSFQ-14 total score > 47 for men and > 41 for women) at Baseline to abnormal (ie, CSFQ-14 total score ≤ 47 for men and ≤ 41 for women), and CSFQ-14 negative responders (decrease from Baseline in CSFQ-14 total score ≥ 3) will be analyzed at all visits by logistic regression, adjusting for baseline CSFQ-14 total score, sex, and treatment.

PGI-I will be analyzed by study visit using ANCOVA and LOCF, with treatment, center, and sex as fixed factors.

C-SSRS will be summarized by study visit for each treatment group using descriptive statistics.

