4.4 Study Design

This is a Phase 4, multicenter, randomized, double-blind, placebo- and active-controlled (paroxetine), 4-arm, parallel group, fixed-dose study comparing the effect of vortioxetine (10 and 20 mg QD) vs paroxetine (20 mg QD) on sexual functioning after 5 weeks of treatment in healthy adult men and women. This outpatient study will be conducted at approximately 15 sites in North America. Men and women will be enrolled in approximately equal proportions (ie, 50% men and 50% women, overall). Enrollment will be capped for each sex when the enrollment target has been met for that sex stratum.

After providing informed consent, subjects will be assessed for study eligibility during a Screening Period of up to 4 weeks. Healthy subjects who have normal sexual functioning (as defined by the CSFQ-14), have been in a steady relationship for ≥ 3 months, are currently sexually active, and meet all other study entry criteria will be enrolled. At Baseline (Day 0), eligible subjects will be equally (1:1:1:1) randomized to double-blind vortioxetine 10 mg,

[figure not shown]
vortioxetine 20 mg, paroxetine 20 mg, or placebo and will be treated for 5 weeks. Randomization will be stratified by sex. Subjects allocated to vortioxetine 20 mg will initiate treatment at 10 mg/day for the first week. Subsequently, the dose will be increased to 20 mg/day and remain at 20 mg/day until study completion. Subjects allocated to vortioxetine 10 mg will initiate treatment at 10 mg/day and remain at 10 mg/day until study completion. Subjects allocated to paroxetine 20 mg will initiate treatment at 20 mg/day and remain at 20 mg/day until study completion. Subjects will be instructed to take their first dose of study drug the day after baseline on Day 1, preferably in the morning. After randomization, subjects will be seen for weekly visits and receive a follow-up safety contact 2 weeks after the end of double-blind treatment. At the end of 5 weeks of treatment, or at early termination, all subjects will abruptly discontinue study drug.

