Sexual functioning will be assessed at each study visit using the CSFQ-14 (primary variable). The PGI-I scale will be administered at each study visit during the double-blind Treatment Period and at the Final Visit. Signs of suicidal risk will be assessed at each study visit using the C-SSRS and the investigator's clinical judgment. Safety will be assessed throughout the study. A total of 6 sparse pharmacokinetic (PK) samples (trough samples) will be collected to measure plasma vortioxetine or paroxetine concentrations at Weeks 3, 4, and 5/ET (2 samples at each time point). A PGx blood sample for deoxyribonucleic acid (DNA) isolation will be collected at Baseline (Day 0), and 2 PGx blood samples for ribonucleic acid (RNA) isolation will be collected at Baseline (Day 0) and also at Week 5/ET.

The end of the study is defined as the date the last subject completes the Final Visit (Week 5).

A schematic of the study design is presented in [Figure 4.a](#). A schedule of study procedures is provided in [Appendix A](#).

Figure 4.a Schematic of Study Design

Note: The Follow-up Contact will be conducted by telephone.

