7.9.2 Missing Items on Rating Scales

Missing values for post-baseline assessments will be imputed by the last observed value immediately prior to the missing value carried forward (LOCF). This rule does not apply to individual items in a multiple-item assessment. LOCF is used after imputation, ie, LOCF values are not used for calculations of subscale/scale scores.

The general rule when individual items are missing from a multiple-item assessment is as follows: the total score will be calculated using a SAS function CEIL, as $\text{CEIL}[(\text{sum of nonmissing items}) \times (\text{total number of items}) / (\text{number of nonmissing items})]$. If more than 20% of the items are missing, the total score will be set to missing. The implications of this rule are indicated in [Table 7.c](#) for each rating scale. The resulting calculated total scores will be used in all analyses.

Table 7.c Number of Missing Items on Rating Scales Associated with a Missing Value

CONFIDENTIAL

for Total Score

Parameter	Number of Missing Items
CSFQ-14	≥ 3
CSFQ _i or CSFQ dimension or CSFQ 3-phases	≥ 1

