7.9.4 Secondary Efficacy Endpoints

Change from Baseline in CSFQ-14 total score for vortioxetine (10mg and 20mg separately) vs paroxetine, paroxetine vs placebo, and vortioxetine vs placebo at each visit will also be analyzed using ANCOVA and LOCF, with treatment, center, and sex as fixed factors, and baseline CSFQ-14 total score as covariate. MMRM method will also be used in sensitivity analyses. Similar analyses will also be performed for the male and female subgroups. Comparisons to placebo will be made at the significance level of 0.05 outside of multiplicity control.

The percentage of subjects meeting criteria for sexual dysfunction (ie, CSFQ-14 total score \leq 47 for men and \leq 41 for women) at any visit (using both LOCF and OC) during the double-blind Treatment Period will be analyzed by logistic regression, adjusting for baseline CSFQ-14 total score, sex, and treatment.

The following SAS code will be used for the logistic regression analysis:

```
Proc logistic data=all descending;
  - class treat;
  - model resp = treat baseline sex;
```

In the above model, Baseline is the baseline value for the corresponding response variable.

In addition, the sex effect on sexual dysfunction will also be investigated by the inclusion of the sex-treatment interaction term and the sex subgroup analysis.

Change from Baseline in CSFQ-14 subscales 5 dimensions, 3 phases, and individual items of the sexual response cycle will be analyzed at all visits using ANCOVA (LOCF) and MMRM similar to the primary analysis.

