Appendix A Schedule of Study Procedures

Study Day/Week:	Screening Period	Base-line	Double-Blind Treatment Period					Final Visit/ET Visit (a)	Follow-up Contact (b)
	Days -28 to -1	Day 0	Week 1	Week 2	Week 3	Week 4	Week 5	Week 7	
Visit Windows (Days Relative to Baseline [Day 0]):		0	±3	±3	±3	±3	±3	±5	
Visit Number:	1	2	3	4	5	6	7		
Screening/Baseline Procedures									
Informed consent	X								
Subject registry database	X								
Demographics, medical and/or psychiatric history, medication history	X								
Height, BMI	X								
ECG	X								
HBsAg, HCV, HIV, free testosterone, TSH, free T4, HbA1c (c)	X								
Urine drug screen	X	X							
Concurrent medical and psychiatric conditions	X	X (d)							
Inclusion/exclusion criteria	X	X (d)							
Eligibility verification	X	X (e)							
Safety Assessments									
Physical examination, weight	X	X					X		
Vital signs	X	X		X			X		
Concomitant medications	X	X	X	X	X	X	X	X	
Hematology, serum chemistry, urinalysis	X	X (f)					X (f)		
C-SSRS	X	X	X	X	X	X	X		
PTE assessment (g)	X	X							
AE assessments (h)			X	X	X	X	X	X	
Pregnancy test (hCG) (i)	X	X	X	X	X	X	X		
Sexual Functioning Assessments									
CSFQ-14 (j)	X	X	X	X	X	X	X		
PGI-I (j)			X	X	X	X	X		
Other Blood Sampling									
PK sample collection (k)					X	X	X		
DNA PGx sample collection (l)		X							
RNA PGx sample collection (m)		X					X		
Clinical Supplies									
Contact IWRS for subject ID/medication ID/subject status	X	X	X	X	X	X	X		

CONFIDENTIAL

Study Day/Week:	Screening Period	Base-line	Double-Blind Treatment Period				Final Visit/ET Visit (a)	Follow-up Contact (b)
	Days -28 to -1	Day 0	Week 1	Week 2	Week 3	Week 4	Week 5	Week 7
Study drug compliance technology		X	X	X	X	X	X	
Dispense study drug		X (n)	X	X	X	X		
Study drug return/accountability/compliance			X	X	X	X	X	

(a) Final Visit procedures to be conducted for subjects who withdraw early, except for those who withdraw their consent and refuse further contact.

(b) The Follow-up Contact will be conducted by telephone.

(c) TSH to be measured at Screening to exclude subjects with clinically significant thyroid dysfunction (hyperthyroidism or hypothyroidism), which may impact sexual functioning. If TSH value is outside the normal range, free T4 will be measured.

(d) To be updated at Baseline.

(e) A prerandomization form must be approved by the PPD medical monitor prior to randomization.

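### Dysfunction at 2 consecutive visits is scored on LOCF data only, so one abnormal score followed by a missing visit counts as two, and no planned analysis of this endpoint shows how often

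*SAP*

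**What the plan says.** Dysfunction is a CSFQ-14 total at or below 47 for men or 41 for women. SAP 5.3 and Protocol 5.2.3 list its occurrence at two consecutive visits as an additional endpoint. The protocol's analysis (13.1.3.3) is "at any 2 consecutive visits (using LOCF) during the double-blind Treatment Period will be analyzed by logistic regression", and SAP 7.9.5 repeats it: "at any 2 consecutive visits (using LOCF) during the treatment period will be analyzed by logistic regression". Neither names a second data handling for this endpoint.

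The imputation rule is general. SAP 7.9.2: "Missing values for post-baseline assessments will be imputed by the last observed value immediately prior to the missing value carried forward (LOCF"). It does not separate a missed visit from dropout, makes no exception for this endpoint, and does not require both visits of a pair to be observed.

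The related secondary endpoint is treated differently. SAP 7.9.4 analyses dysfunction "at any visit (using both LOCF and OC) during the double-blind Treatment Period".

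CSFQ-14 is collected weekly, last at Week 5. For early leavers, SAP Appendix A note (a) has "Final Visit procedures to be conducted for subjects who withdraw early", which includes CSFQ-14. SAP 7.1.3 assigns a score on Day 32 or later to the Week 5 window and earlier scores to earlier windows.

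**The concern.** What the two-consecutive-visit definition adds to the any-visit definition is a repeat of the abnormal score. Once carried-forward values may supply the repeat, that requirement disappears for anyone whose first abnormal score is followed by a gap. Two subjects with the same observed dysfunction can then be classified differently because one kept attending and the other did not.

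The outcome is a harm, and adverse events are a listed reason for discontinuation (Protocol 7.4), so dropout could plausibly follow dysfunction or differ between arms. If it did, part of an arm's percentage on this endpoint would reflect missing visits, and nothing planned for the endpoint would let a reader see how much.

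**Working it through.** **Plan's own figure.** The documents give no rate, power or sample size for this endpoint, and no dropout rate. The one sizing statement (88 per arm, SD 8.5, difference 4.0) concerns the primary endpoint and is not in question here.

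**Step 1: apply the written rule.** Weeks 1 to 5; 1 = abnormal, 0 = normal, . = missing.

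| Observed | After LOCF | Counted under LOCF | Counted on observed scores |
|---|---|---|---|
| 0 1 . . . | 0 1 1 1 1 | yes | no |
| 1 . . . . | 1 1 1 1 1 | yes | no |
| 0 0 0 1 . | 0 0 0 1 1 | yes | no |
| 0 1 . 0 0 | 0 1 1 0 0 | yes | no |
| 0 1 0 0 0 | 0 1 0 0 0 | no | no |
| 0 0 0 0 1 | 0 0 0 0 1 | no | no |

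The fourth and fifth rows have the same single abnormal score. They differ only in whether Week 3 was attended.

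**Step 2: the any-visit endpoint.** Copying an abnormal score forward cannot turn a subject who was never abnormal into one who was. LOCF and observed-case data therefore classify each subject alike on that endpoint. The observed-case check sits where LOCF changes nothing and is absent where it does.

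**Step 3: size, by simulation.** All inputs are assumptions: an abnormal rate of 10%, 20% or 30% at each visit; within-subject correlation (rho) 0.5 or 0.7; dropout of 10% or 20%. The latent score at visit k is sqrt(rho) × u + sqrt(1 − rho) × e_k, with u and e_k standard normal, and is abnormal below the matching normal quantile. Both versions keep all subjects in the denominator. Anyone counted on observed scores is also counted under LOCF, so:

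- share counted on one observed score = LOCF rate − observed rate
- net error of each version = its rate − complete-data rate

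With dropout unrelated to score, no missed visits and rho 0.5 (percent of arm; small discrepancies are rounding):

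| Abnormal per visit | Dropout | Complete data | LOCF | Observed only | On one score |
|---|---|---|---|---|---|
| 10% | 10% | 8.0 | 8.3 | 7.6 | 0.7 |
| 10% | 20% | 8.0 | 8.6 | 7.1 | 1.5 |
| 20% | 10% | 18.9 | 19.2 | 18.0 | 1.3 |
| 20% | 20% | 18.9 | 19.6 | 17.0 | 2.6 |
| 30% | 10% | 30.8 | 31.1 | 29.3 | 1.7 |
| 30% | 20% | 30.8 | 31.4 | 27.9 | 3.5 |

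In the last row, LOCF errs by 31.4 − 30.8 = +0.6 points and observed-only by 27.9 − 30.8 = −2.9.

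Next, 3% missed visits were added, both correlations were used, and the chance of leaving was either unrelated to score or tripled after an abnormal score. Ranges over all scenarios:

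- counted on one observed score: about 1-8% of an arm, i.e. 0.01 × 88 to 0.08 × 88, about 1 to 7 subjects
- LOCF against complete data: +0.4 to +2.9 points
- observed-only against complete data: −0.7 to −5.0 points

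**The case against.** The strongest objection is that the obvious remedy, counting only two observed scores, also classifies by dropout, with the opposite sign. It treats everyone who leaves after one abnormal score as unaffected, although many would have been abnormal again. With the chance of leaving tripled after an abnormal score and no missed visits, observed-only was further from the complete-data rate than LOCF in 10 of 12 scenarios. For a harm outcome that could hide dysfunction in the arm losing subjects because of it. This stands, and it rules out simply replacing LOCF.

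A reader might also infer a false between-arm difference of 2-4 points: with 20% dropout in one arm, 10% in another, and 20-40% of leavers first abnormal at their last score, (20% − 10%) × 20-40% = 2-4 points. The documents do not support that. They give no dropout by arm and no source for the 20-40%, and the product treats every such leaver as wrongly counted. With equal dysfunction in both arms, the simulated gap in LOCF rates between 20% and 10% dropout was 0.2-0.4 points when dropout was unrelated to score, and about 1 point when leaving was tripled after an abnormal score.

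There is partial mitigation. An early-termination CSFQ-14 can supply a second observed score if it falls in the next window. Dysfunction is also analysed at any visit, as a shift at each visit, and by Cox model with Kaplan-Meier plots. Listings show CSFQ-14 by windowed visit, so the affected subjects could be found by hand. The LOCF rule is prespecified and agrees between the documents. All of this lowers the stakes. None of it is a planned observed-case result or count for this endpoint.

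**Conclusion.** The point holds as one of transparency in an additional endpoint. As written, a single abnormal score followed by a missing visit before Week 5 satisfies a two-visit criterion, and no planned analysis of that endpoint reveals it. The sizes in the working rest wholly on assumed dropout, missed-visit and dysfunction rates, so they show plausible scale rather than a prediction. Whether a treatment comparison would be biased, and in which direction, cannot be said from the documents.

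It might be inferred that LOCF is also why a completer first abnormal at Week 5 goes uncounted. It is not: CSFQ-14 follow-up ends at Week 5, so there is no later visit to pair with, and an observed-case rule leaves that subject uncounted too. LOCF explains only the contrast with someone who leaves earlier on one abnormal score.

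The endpoint has no multiplicity control (SAP 7.1.2) and no part in the sizing. The matter is minor and cheap to settle.

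**What to change.** Keep the LOCF analysis, so Protocol 13.1.3.3 can stand. Add to SAP 7.9.5, before unblinding:

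1. A prespecified observed-case version. A subject qualifies only if two adjacent scheduled visits both have an observed CSFQ-14 total at or below the sex-specific cut-off. Use the same logistic model and keep all FAS subjects in the denominator, so that the two percentages are comparable.
2. A statement that the LOCF and observed-case results are reported together as the upper and lower readings. They are not strict bounds on the complete-data rate: a subject who leaves while still normal and would later have become abnormal is missed by both.
3. A table row giving, by arm, the number of subjects who qualify under LOCF on a single observed abnormal score.

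The cost is a few lines of SAP text, one extra logistic regression and one table row. The downside is that the observed-case percentages will be lower and will treat leavers with one abnormal score as unconfirmed; the table row shows how many they are.

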7.1.3 Definition of Study Day and Study Visit Windows

A windowing convention will be used to determine the analysis value for a given study visit that applies to observed data.

Study Day -1 corresponds to the date of the Baseline visit, ie, the randomization date. Other study days are defined relative to Study Day 1, the date of first double-blind study drug dose. Relative day is calculated as (date of interest – date of first dose +1) for study days on or after the

date of first dose and as (date of interest – date of first dose) for study days prior to the first dose date.

For each visit, a window will be defined such that the lower and upper bounds of each window is generally the midpoint between 2 consecutive study visits. The visit windows and applicable study day ranges are presented below in [Table 7.a](#).

Table 7.a Visit Windows

Nominal Visit Week	Nominal Visit Day	CSFQ-14, PGI-I, C-SSRS	Vital signs	Lab, PE,Weight,	PK
Baseline	-1 (a)	≤1 (b)	≤1	≤1	≤1 (b)
1	7	2 – 10			
2	14	11 – 17	2-24		
3	21	18 – 24			2-24
4	28	25 – 31			25-31
5	35	≥32	≥25	≥2	≥32
7	49				

(a) Baseline day has been defined as Day -1 in keeping with Clinical Data Interchange Consortium standards. There is no Day 0.

(b) No baseline assessment for PGI-I or pharmacokinetic (PK) sampling.

More than 1 result for a parameter may be obtained in a visit window. In such an event, the result with the date closest to the scheduled visit day will be used. In the event of 2 observations equidistant to the scheduled visit day, the later of the observations will be used. Treatment Period Last Visit values will be defined irrespective of falling in a particular window. Hence, the windowed Week 8 value may be different than the Last Visit value.

In general, the baseline value for a variable is defined as the last observation prior to the first dose of double-blind study medication (visit date \leq first dose date), including the screening value, if necessary.

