7.9.3 Primary Efficacy Endpoint(s)

Mean change from Baseline in the CSFQ-14 total score difference for vortioxetine vs paroxetine after 5 weeks of treatment will be the primary endpoint. The primary analysis will be based on analysis of covariance (ANCOVA) using the last observation carried forward (LOCF) technique, with treatment, center, and sex as fixed factors, and baseline CSFQ-14 total score as covariate. The comparisons will be between each vortioxetine dose (10 or 20 mg) and paroxetine, and both statistical tests will be 2-sided.

The following example SAS code will be used for the ANCOVA analysis:

```
Proc mixed data=all;
  - class treat center sex;
  - model Change= Baseline treat center sex;
  - lsmeans treat;
```

In the above model, Baseline is the baseline value and Change is the change from baseline value.

The Holm-Bonferroni method will be used to adjust for multiplicity and control the familywise type I error rate at a significance level of 0.05. If the smaller of the 2 P-values is <0.025 , significance is obtained for the associated vortioxetine dose and the other dose will then be evaluated at a 0.05 significance level. Although vortioxetine will be compared with paroxetine in the primary analysis, paroxetine will also be compared with placebo to validate the study. The primary analyses will also be repeated based on the PPS if more than 5% of the total subjects in the FAS have major protocol violations.

As supportive analyses, the sex-by-treatment interaction term will be added to the primary analysis model to further check the sex effect on the treatment. The similar ANCOVA analyses will also be performed using the observed case (OC) data.

Change from Baseline in the CSFQ-14 total score will also be analyzed based on a mixed model for repeated measurements (MMRM) with treatment, center, week, treatment-by-week interaction and sex, as fixed effects, and baseline CSFQ-14 total score, and CSFQ-14 total score-by-week as covariates. The effect at each time point for each treatment is allowed to vary freely and an unstructured covariance matrix is assumed.

The SAS code for the MMRM analysis will be as follows:

```
Proc mixed data=all;
  - class week treat center subject;
  - model Change = baseline*week baseline treat center week week*treat sex /solution;
  - repeated week/subject=subject type=UN;
  - lsmeans week*treat / cl pdiff.
```

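### The Cox model for time to sexual dysfunction leaves out baseline CSFQ-14, which the logistic model of the same event includes; the test is valid but may lose some power (minor)

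*SAP*

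**What the plan says.** SAP 7.9.5 covers two time-to-event outcomes: time to sexual dysfunction and time to a CSFQ-14 negative response. Each "will be analyzed using a Cox model with an exact method to handle ties, with treatment and sex as factors". The code has the same two terms: "model T_Sexdys*status_1(0) = treat sex/ ties=exact". Protocol 13.1.3.3 gives the same two-factor model for dysfunction ("Time to sexual dysfunction as assessed by the CSFQ-14 will be analyzed using a Cox model with an exact method to handle ties") and does not mention time to negative response.

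The other models of CSFQ-14 total-score outcomes carry the baseline score:

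- Primary ANCOVA (SAP 7.9.3): "model Change= Baseline treat center sex". The MMRM in the same section has baseline and baseline-by-week terms.
- Dysfunction at any visit (SAP 7.9.4): logistic regression "adjusting for baseline CSFQ-14 total score, sex, and treatment", coded as "model resp = treat baseline sex".
- Dysfunction at two consecutive visits, shift to abnormal, and negative response by visit (SAP 7.9.5): logistic regression with the same three terms.

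PGI-I is also modelled without a baseline term, but there the reason is visible in the footnote to SAP Table 7.a: "No baseline assessment for PGI-I or pharmacokinetic (PK) sampling". No reason is given for the Cox model. The covariate exploration at the end of SAP 7.9.3 concerns the primary ANCOVA only, so no planned analysis adds baseline to the Cox model.

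**The concern.** The event is a fall to a fixed cut-off: 47 or below for men, 41 or below for women (SAP Table 7.b). Inclusion criterion 8 requires every subject to start above that cut-off. A subject who enters 2 points above it is much closer to an event than one who enters 15 points above, so baseline is the obvious prognostic variable.

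The any-visit logistic analysis and the Cox analysis describe the same crossings, one without timing and one with it. LOCF does not separate them, because a carried-forward abnormal score was already an event when it was observed. Yet one analysis is adjusted for baseline and the other is not. If their results diverge, it will be unclear whether timing or adjustment is responsible.

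Randomization protects the treatment test, so bias in that test is not the issue. What is at stake is efficiency, a hazard ratio that tends to lie closer to 1 than its baseline-conditional counterpart, and comparability of the two analyses.

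**Working it through.** **1. The plan's own power figure (protocol 13.3, SAP 6.0).** Inputs: 88 per arm, SD 8.5, difference 4.0, two-sided 0.025.

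- Standardized difference: 4.0 / (8.5 × √(2/88)) = 4.0 / 1.281 = 3.12.
- Critical value 2.24, so power is Φ(3.12 − 2.24) = Φ(0.88) = 81.1%, or 80.4% with the noncentral t.
- Under Holm, with two comparisons sharing the paroxetine arm (correlation 0.5), simulated power per dose is 85.5%.

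These match the stated ≥80% and approximately 85%. The plan gives no power, event count or hazard ratio for the Cox analysis.

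**2. Whether the total score is the right term.** The distance to the event is baseline − 41 for women and baseline − 47 for men, that is, baseline − 41 − 6 × (male). With sex in the model, adding the baseline total score is equivalent to adding this distance.

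**3. When baseline should help.** Let β be the slope of change on baseline. The follow-up score is baseline plus change, so its mean given baseline has slope 1 + β. At β = 0 baseline carries over fully; at β = −1 it says nothing about the follow-up score and adjustment should gain nothing. For negative response the event depends on the change itself, so baseline should matter only when β differs from 0.

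**4. Simulation.** Four arms, half men, 1,000 trials per scenario.

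- From the documents: 88 per arm, change SD 8.5, difference 4.0, cut-offs, five weekly visits.
- Assumed: baseline margin above the cut-off truncated at 1 point, with mean/SD 8.3/3.7, 8.9/4.7 or 10.8/6.1; β of 0, −0.25, −0.5 or −1; between-visit residual correlation 0.5 or 0.8.
- Also assumed: paroxetine 4.0 points worse than each other arm, phased in as 50%, 80%, 100%, 100%, 100% over Weeks 1 to 5; dropout 3% per visit (1 − 0.97⁵ = 14% by Week 5).
- Analysis: exact handling of ties, two-sided Wald test at 0.05, treatment + sex against treatment + sex + baseline.

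Power for vortioxetine 20 mg vs paroxetine on time to dysfunction (six scenarios per row; simulation SE of a difference at most 1.5 points):

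| Slope β | Gain from adding baseline | Examples |
|---|---|---|
| 0 | +5 to +11 points | 58% to 63%; 51% to 62% |
| −0.25 | +2 to +9 points | 54% to 57%; 58% to 64% |
| −0.5 | +1 to +4 points | 58% to 59%; 67% to 71% |
| −1 | −0.2 to +0.5 points | about no change |

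At β = 0 a hazard ratio of about 1.6 becomes about 1.65 to 1.7.

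**5. Type I error.** With no treatment difference, over 8,000 trials, rejection is 5.4% without and 5.7% with baseline (SE about 0.24 points). Baseline effects were not forced to be proportional over weeks.

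**6. Check under different assumptions.** Two arms, Efron ties, no dropout, margin 8 to 11 with SD 5 to 7 before truncation, baseline–change correlation 0 to −0.5, between-visit correlation 0.6. Over nine settings, power rises by 0.3 to 7.8 points (39.3% to 47.1% at the largest, 74.1% to 74.4% at the smallest). Null rejection without baseline is 4.4% to 5.8%.

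**7. Time to negative response.** Average gains are 0, +1 and +3 points at β = 0, −0.25 and −0.5. The pattern is the reverse of that for dysfunction, as step 3 predicts.

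**The case against.** The strongest reply is that nothing here is an error. Protocol and SAP agree, treatment plus the stratification factor is a standard prespecified Cox model, and the plan does not use one covariate set throughout: center is in the ANCOVA and MMRM but in neither the logistic nor the Cox models. Baseline-adjusted analyses of the same cut-off are already planned for any visit, for two consecutive visits and for shift at each visit. All of this stands and is why the point is minor.

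The size is also open to challenge. If 8.5 is the SD of change and s₀ the baseline SD, the follow-up variance is s₀² + 72.25 + 2βs₀². At β = 0, baseline SDs of 3.7, 4.7 and 6.1 imply follow-up SDs of 9.3, 9.7 and 10.5, which are 2.5, 2.1 and 1.7 times baseline. Equal SDs at both times would need β = −72.25 / (2 × 6.1²) = −0.97 or steeper, where the gain is about 0. Eligibility truncates baseline, so some widening is plausible, but the top of the range also needs no regression to the mean after selection on a cut-off. The 11-point figure is therefore an upper end, not an expectation.

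Two further points are fair. The shift in the hazard ratio is partly non-collapsibility, a change of target rather than removal of bias. And the added term brings a linearity and a proportional-hazards assumption for baseline; the null check covers type I error but not interpretation of the conditional hazard ratio.

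None of this gives a reason to leave baseline out. No scenario showed a material loss from including it, and the variable is already in the parallel models.

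**Conclusion.** The concern holds, as a minor one. The Cox model omits a prognostic covariate that the logistic model of the same event includes, with no stated reason. The planned test is valid and the documents do not contradict each other. The direction is firm: some power may be lost. The amount is not, because the documents give neither the baseline SD nor the relation of change to baseline. Over the assumptions examined it runs from nothing to about 11 points, with 1 to 9 points at slopes between −0.25 and −0.5. The endpoint is additional (SAP 5.3), its tests are nominal (SAP 7.1.2), and no confirmatory conclusion depends on it. No power argument is made for time to negative response.

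**What to change.** Before unblinding, change SAP 7.9.5 as follows.

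- Code: `model T_Sexdys*status_1(0) = treat sex baseline / ties=exact;`, with baseline as a continuous term.
- Text: add baseline CSFQ-14 total score as a covariate, next to treatment and sex.
- Interpretation: state that the hazard ratio is conditional on sex and baseline CSFQ-14 total score, and is a different estimand from the ratio without baseline (non-collapsibility).
- Plots: the SAP says "The analysis will also be supplemented with plots of Kaplan-Meier estimates of sexual dysfunction". Add that these are unadjusted and descriptive.
- Time to negative response: use the same term, only for consistency with its visit-by-visit logistic model.
- SAP 7.15: record the departure from protocol 13.1.3.3.

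The cost is one model term, two sentences and a line in 7.15. Baseline CSFQ-14 is already collected and already used in the ANCOVA, MMRM and logistic models. Made after unblinding, the same change would be post hoc.
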